### **6.12.3. Deaths, Other Serious Adverse Events, and Other Notable Adverse Events**

Treatment-emergent adverse events by Preferred Term will be reported.

The general summary of AEs is described in the CPMP SAP Version 5.

### **6.12.4. Clinical Laboratory Evaluation**

The general analysis of laboratory parameters is described in the CPMP SAP Version 5.

In this ISA, laboratory results will be reported for the first 4-week, active-treatment period and separately for the entire 8-week study period.

Study NP02 will also consider the following analyses of lab analytes used to assess renal function. The planned summaries for these analytes are the same as those that have been described in the Study CPMP SAP Version 5; however, the reporting of these analytes will be separate from the general analysis of laboratory parameters.

Renal data analyses:

- Serum creatinine (change from baseline in mg/dL)
- Estimated glomerular filtration rate (eGFR; Chronic Kidney Disease Epidemiology Collaboration [CKD-EPI] algorithm using serum creatinine) Algorithm: Provided by central laboratory
- For eGFR calculation, we will summarize shift tables of eGFR changes for baseline vs. postbaseline by minimum, maximum and last observed eGFR result:
  - Category 1: Normal or increase in GFR ( 90 mL/min/1.73m^2)
  - Category 2: Mild reduction in GFR (60 to 89 mL/min/1.73m^2)
  - Category 3a: Moderate (a) reduction in GFR (45 to 59 mL/min/1.73m^2)
  - Category 3b: Moderate (b) reduction in GFR (30 to 44 mL/min/1.73m^2)
  - Category 4: Severe reduction in GFR (15 to 29 mL/min/1.73m^2)
  - Category 5: Kidney failure (GFR < 15 mL/min/1.73m^2 or dialysis).

Abnormal eGFR is specified below and will be summarized in the laboratory summary tables.

- Abnormal low: < 90 mL/min/1.73m^2
- Abnormal high: As specified by central laboratory.

#### **6.12.5. Vital Signs and Other Physical Findings**

The analysis of vital sign parameters is described in the CPMP SAP Version 5.

Vital signs will be reported for the first 4-week, active-treatment period, and separately for the entire 8-week study period.

#### **6.12.6. Electrocardiograms**

The analysis of electrocardiogram parameters is described in the CPMP SAP Version 5.

Electrocardiogram will be reported for the first 4-week, active treatment period and separately for the entire 8-week study period.

#### **6.12.7. Suicidal Ideation or Behavior**

Reporting of suicidal ideation/behavior through the Columbia Suicide-Severity Rating Scale (C-SSRS) has been described in the CPMP SAP Version 5. C-SSRS will additionally be reported separately for the first 4-week active treatment period.

### **6.13. Subgroup Analyses**

General subgroup analyses are described in the CPMP SAP Version 5.

The subgroup analyses will be conducted using similar modeling approaches as the primary analyses. Additional factors in the model are described in the CPMP SAP Version 5. The treatment difference at the endpoint will be reported within each level of the subgroup factor along with 95% credible intervals. Frequentist MMRM may be performed as a sensitivity analysis using the modeling approach described in the CPMP SAP Version 5.

## 6.14. Protocol Deviations

Participants with study important protocol deviations will be summarized by type of deviation and listed by treatment and investigative site.

Important protocol deviations for the study are described in the CPMP and Study NP02 Trial Issue Management Plans.

## 6.15. Interim Analyses and Data Monitoring

Safety review will be conducted under the auspices of an Assessment Committee according to the specifications set forth in the protocol. These analyses will be at the CPMP level and will consider data from all ongoing ISAs. Details are provided in the CPMP SAP Version 5.

Interim analyses are planned for Study NP02 to be conducted when 60% of patients have the opportunity to complete the 4-week active-treatment period. Details of the interim analysis can be found in the TRPA1 Statistical Analysis Center (SAC) SAP. The interim analysis may change the final sample size from what is planned in this Study NP02 SAP.

Additional interim analyses may be conducted for reasons of futility analyses, early efficacy analyses, safety analyses, or other analyses needed for key business decisions and planning.

## 6.16. Planned Exploratory Analyses

The following analyses may be conducted for exploratory purposes:

### CCI

In addition, a cumulative distribution function of percent change from baseline to endpoint for the following BPI-SF score will be provided for each treatment group.

- Mean interference score
- Mean severity score
- Individual severity scores
- Individual interference scores.

However, no statistical comparisons will be made between the groups.

## 6.17. Totality of Evidence for Safety

The totality of evidence analysis approach for safety data has been briefly described in the CPMP SAP Version 5. This may be reported for any of the active treatment period, post-active treatment period, and entire 8-week study period. The key safety events to be considered for Study NP02 are listed below by domain:

### General Adverse Event Information

- Serious adverse events related to study treatment
- Study discontinuation due to adverse event
- Treatment discontinuation due to adverse event.

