#### **Double-Blind Treatment Period (Visits 3 through 7)**

Each visit is an outpatient visit.

At Visit 3

- participants are randomized to LY3526318 or placebo
- the site completes the NP02 baseline procedures, CCI [REDACTED]  
[REDACTED]
- participants receive their oral study intervention
- the site collects participants vitals at 2 and 4 hours after the completion of the oral administration
- the site completes all post-treatment sample collection and safety monitoring, and
- the site instructs participants to continue with study restrictions and Numeric Rating Scale (NRS) diary entries before their visit discharge.

At Visits 4 through 7

- the site reviews available safety data and completes pre-dose procedures and sample collection
- participants continue oral study intervention (not applicable for V7)
- the site completes all sample collection and safety monitoring noted in the Schedules of Activities (SoAs), and
- the site instructs participants to continue with study restrictions and NRS diary entries before their visit discharge (not applicable for V7).

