## 4. Study Objectives

### 4.1. Primary Objective

The primary objective of this intervention-specific appendix (ISA) is stated in the H0P-MC-CPMP (a) protocol. Additional blinded details regarding LY3526318 dosing that are not included in the protocol can be found in the Ethics Review Board (ERB) supplement for Study NP02. For Study NP02, endpoint is defined as 4 weeks post initial treatment administration at Visit 5. Unless otherwise specified, the time point for secondary endpoint measurements is the same as the primary endpoint.

Objectives	Endpoint
Primary	
Efficacy of LY3526318 versus placebo for pain intensity	Mean change from baseline assessment to 4 weeks for average pain intensity as measured by the NRS

Abbreviation: NRS = Numeric Rating Scale.

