## 5. Study Design

### 5.1. Summary of Study Design

The CPMP protocol provides a summary of the overall study design for the chronic pain master protocol. ISA-specific study design is provided in the NP02 protocol.

In this ISA, patients in the LY3526318 treatment arm receive LY3526318 for the first 4 weeks of the double-blind period (active-treatment period) and switch to placebo for the last 4 weeks of the double-blind period (post-active-treatment period) starting on the day of Visit 5. Placebo patients receive placebo for the entire 8-week double-blind period. Additional details of the study design may be found in the ERB supplement for Study NP02.

For the analyses listed in this SAP, except for treatment compliance, we define active treatment period and post-active treatment period as follows. The first 4 weeks of the double-blind period (active treatment period) ends at the day of Visit 5. The last 4 weeks of the double-blind period (post-active treatment period) begins the day after Visit 5.

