**Cardiovascular**

QTc prolongation: >60 msec increase  
Serious cardiac disorders adverse event.

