**Metabolic function**

Serious hypoglycemia adverse event

Treatment-emergent HbA1c: Shift from low/normal at baseline to high at least once.

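### The key-event safety summary in SAP 6.17 counts general SAEs only when judged related to treatment, so a death or SAE judged unrelated can be missing from that summary

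*SAP*

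**What the plan says.** SAP 6.17 lists key safety events by domain. The general domain has three items: "Serious adverse events related to study treatment", "Study discontinuation due to adverse event", and the matching item for discontinuation of treatment. It has no item for SAEs of any cause and none for deaths. Two later domains contain serious-event items without a relatedness condition: "Serious cardiac disorders adverse event" and "Serious hypoglycemia adverse event". The remaining items are a QTc criterion and laboratory criteria for liver, HbA1c and eGFR.

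The summary is optional and its period is left open: "This may be reported for any of the active treatment period, post-active treatment period, and entire 8-week study period".

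SAP 5.1 says that participants in the LY3526318 arm "switch to placebo for the last 4 weeks of the double-blind period (post-active-treatment period) starting on the day of Visit 5". SAP 4.1 adds: "Additional blinded details regarding LY3526318 dosing that are not included in the protocol can be found in the Ethics Review Board (ERB) supplement". The visible protocol text (section 4.1, Visits 4 through 7) says only that "participants continue oral study intervention (not applicable for V7", and mentions no switch.

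**The concern.** Whether an SAE enters the general item depends on a case-by-case causality judgement. SAP 6.17 does not say who makes it or by what rule. The protocol synopsis describes a randomised trial with investigators and participants blind, so the placebo arm already shows the background rate of serious events, and the arms can be compared without any such judgement. The events most exposed to the filter are unexpected drug effects that look like comorbidity in people with diabetes. A pneumonia, a fall or a stroke called unrelated is an example.

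The list is also uneven. A serious cardiac event counts whatever its judged cause, but a serious infection does not.

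The switch at Visit 5 makes matters somewhat worse. An assessor who has only the visible protocol text would regard a participant in Weeks 5 to 8 as possibly on drug, when every participant is on placebo. What is at stake is how visible a safety signal is in this one summary.

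**Working it through.** **Tracing an event.** Take an SAE, possibly fatal, that is judged unrelated, is not a cardiac disorder and is not hypoglycemia.

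- SAP 6.17, general SAE item: not counted, because it was not judged related.
- SAP 6.17, discontinuation items: counted only if the event led to discontinuation of study or treatment. Whether a death is recorded that way is not stated.
- SAP 6.17, cardiac and hypoglycemia items: not counted.
- SAP 6.17, QTc, liver, HbA1c and eGFR items: counted only if a criterion happens to be met.
- SAP 6.19: counted by treatment group and Preferred Term, with no relatedness filter and regardless of treatment emergence.
- SAP 6.12.3: Preferred Term reporting of treatment-emergent events, with the general summary left to the master SAP (CPMP SAP Version 5).

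So the event can be absent from 6.17 and still appear in 6.19.

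**What the filter does to the comparison.** The plan gives no SAE rate and no share judged related, so it has no figure of its own on this point to reproduce. Let the background risk be b in both arms and the drug-caused excess be d. Let the shares called related be r for background events and s for drug-caused events, with r equal across arms because assessment is blinded. Then:

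- active arm counted: r·b + s·d
- placebo arm counted: r·b
- difference: s·d

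The absolute difference shown is the true excess multiplied by s. It cannot exceed the unfiltered difference, and it equals it only if every drug-caused SAE is called related.

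**Illustration, with all rates assumed.** About 150 participants are planned (SAP 5.2). The allocation ratio is redacted, so 75 per arm is an assumption. Assume SAE risks of 6% (active) and 2% (placebo), and the same share s called related for all SAEs in both arms. Expected counts are 75 × 0.06 × s and 75 × 0.02 × s. The chance that no active-arm participant is counted is (1 − 0.06 × s)^75. Power is approximate, for a two-sided 5% comparison of two proportions.

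| Share called related | Active counted | Placebo counted | Risk difference | Chance of zero in active arm | Power |
|---|---|---|---|---|---|
| 100% (no filter) | 4.5 | 1.5 | 4.0 points | 0.94^75 = 1% | 24% |
| 50% | 2.25 | 0.75 | 2.0 points | 0.97^75 = 10% | 14% |
| 25% | 1.13 | 0.38 | 1.0 point | 0.985^75 = 32% | 9% |
| 10% | 0.45 | 0.15 | 0.4 points | 0.994^75 = 64% | 6% |

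With 100 active and 50 placebo, the chance of zero in the active arm runs 0.2%, 5%, 22% and 55%. Power is low in every row, so the loss is one of visibility and not of a powered test. With an equal share in both arms the risk ratio stays at 3. The counts and the absolute difference are what shrink.

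**Weeks 5 to 8.** By SAP 5.1 the switch covers 4 of the 8 double-blind weeks, and SAP 6.17 allows reporting for that period or for all 8 weeks. SAP 6.12.2 summarizes post-active-treatment-emergent events only in participants who received LY3526318. That makes an unfiltered count by arm for this period more useful.

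**The case against.** The strongest reply is that 6.17 is not the trial's safety comparison. It is an optional summary whose method is set out in CPMP SAP Version 5. SAP 6.19 tabulates every SAE by treatment group and states that this reporting agrees with the clinical study report. SAP 6.18 adds a cumulative SAE summary and a list of deaths, pooled across LY3526318 studies, and SAP 6.15 provides for committee safety review. This stands. A reader might infer that deaths and SAEs judged unrelated leave the randomised safety comparison altogether. The documents do not support that, and the master SAP, which may hold further all-cause tables, is not available to check.

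A second reply is that a related-only item limits background noise in a diabetic population, and that cardiac and hypoglycemia items are naturally counted regardless of cause. There is something in this: if judgements were accurate, the filter would remove background events at little cost to the excess. But the plan gives no ground for assuming that accuracy, and keeping the related item as a supporting line retains whatever benefit it has.

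A third reply concerns the switch. Withholding it from the protocol is deliberate blinding. Some protocol dosing fields are redacted, the Ethics Review Board supplement is unavailable, and the assessor is not named. A related call in Weeks 5 to 8 is not wrong merely because the capsule is placebo, since delayed or withdrawal effects are possible. The active period can also be reported separately. All of this stands, so the switch is an aggravating factor only. The filter would be questionable without it.

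**Conclusion.** The point holds for the key-event summary in SAP 6.17 and no further. The general SAE item is filtered by judged relatedness, two other serious-event items are not, and there is no all-cause SAE or death item. Under blinded attribution the filter multiplies the absolute difference between arms by the share of drug-caused SAEs called related. In the illustration, 4.0 points become 0.4 to 2.0 for shares of 10% to 50%. Those risks, shares and arm sizes are assumptions; the documents give none of them.

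A reader might also infer that the filter favours one arm, or that the Week 4 switch causes the problem. Neither follows: the documents show no differential attribution, and the switch only makes the Week 5 to 8 judgements harder to read. This is a cheap improvement to one summary, not a gap in SAE reporting.

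**What to change.** In the general domain of SAP 6.17, add an item for serious adverse events, including deaths, regardless of relationship to study treatment. Report it by randomised arm and by period (active, post-active, entire 8 weeks), and give the denominator for each period, since the post-active population in SAP 6.1 leaves out participants who discontinue at or before Visit 5. Keep related SAEs as a supporting item and say who judges relatedness.

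The cost is one line of SAP wording plus that clarification. SAP 6.19 already requires all SAEs, so no new data are needed. The small downside is that background SAEs in both arms are also counted; randomisation balances these in expectation.

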**Cardiovascular**

QTc prolongation: >60 msec increase  
Serious cardiac disorders adverse event.

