#### **8.2.2. Electrocardiograms**

Single 12-lead ECG will be obtained as outlined in the SoA using an ECG machine that automatically calculates the heart rate and measures PR, RR, QRS, QT, and QTcF intervals.

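### SAP 6.17 defines its only QTc key safety event as a rise of more than 60 msec, with no absolute limit and no named correction

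*SAP*

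**What the plan says.** SAP 6.17 refers to the master plan for the method ("The totality of evidence analysis approach for safety data has been briefly described in the CPMP SAP Version 5") and then gives a list specific to this trial: "The key safety events to be considered for Study NP02 are listed below by domain".

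The Cardiovascular domain has two entries, "QTc prolongation: >60 msec increase" and "Serious cardiac disorders adverse event". Neither gives an absolute QTc value, and the first does not say which QT correction applies. Protocol 8.2.2 specifies an ECG machine that "measures PR, RR, QRS, QT, and QTcF intervals", so QTcF is available.

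The General Adverse Event Information domain, in the same list, has three entries that are not tied to an organ system: "Serious adverse events related to study treatment", "Study discontinuation due to adverse event" and "Treatment discontinuation due to adverse event".

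The other laboratory-based entries in 6.17 refer to a level or a category: liver tests against the upper limit of normal, HbA1c moving into the high range, and eGFR moving into a worse band. SAP 6.12.6 leaves the main ECG analysis to CPMP SAP Version 5.

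**The concern.** A change-only rule asks how far a participant moved and ignores where the participant ended up. Someone who starts fairly high can reach a high absolute QTc with a rise too small to count, while someone who starts low can count with an unremarkable final value. QTc is the only measured quantity in the 6.17 list that is judged purely by change.

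The schedule adds to this. The ISA Schedule of Activities has single ECGs at Visits 5 and 7 and at early discontinuation, and none at Visit 3. The baseline for the rule must therefore come from a schedule in the master protocol or the disease-state addendum. A participant with no usable baseline cannot be classified by change, whereas an absolute limit needs no baseline. SAP 5.1 switches the LY3526318 arm to placebo from the day of Visit 5. For a participant who completes the active period, Visit 5 is thus the one ECG in the ISA schedule that falls at its end.

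At stake is whether a short list of key safety events shows a high QTc by arm without the reader having to look elsewhere. The primary efficacy analysis is not affected.

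**Working it through.** **Inputs.** The rule is a rise of more than 60 msec (SAP 6.17, Cardiovascular). The plan states no figure to reproduce. The absolute limit L is an assumption, because the documents give none; 500 msec is used for illustration and 480 msec to show how the result moves.

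**Formula.** Let b be the baseline and v a post-baseline value.
- The plan counts v if v − b > 60.
- A value above the limit is not counted if v > L and v ≤ b + 60.
- Both can hold only if b + 60 > L, that is, b > L − 60.
- For b between L − 60 and L, the uncounted band runs from just above L up to b + 60. Its width is b + 60 − L.

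**L = 500 msec.** The gap opens at b > 500 − 60 = 440.

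| Baseline (msec) | Rise that reaches 500 | Counted only above | Uncounted band above 500 |
|---|---|---|---|
| 440 | 60 | 500 | none |
| 450 | 50 | 510 | 10 |
| 460 | 40 | 520 | 20 |
| 470 | 30 | 530 | 30 |

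In whole milliseconds, a value of 501 from baseline 440 is a rise of 61 and is counted. From 441 the rise is 60 and is not counted. From 460 it is 41 and from 480 it is 21; neither is counted.

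**Two participants compared.** 450 to 505 is a rise of 55: not a key safety event. 370 to 431 is a rise of 61: a key safety event.

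**L = 480 msec.** The gap opens at b > 480 − 60 = 420. At baseline 450 the uncounted band is 450 + 60 − 480 = 30 msec.

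**Serious events, by logic.** Suppose the second cardiovascular entry means the MedDRA Cardiac disorders class. The SAP does not say so, but 6.12.2 uses MedDRA terms and System Organ Classes, which makes the reading plausible. A serious stroke would then be handled as follows:
- judged related to treatment: counted in the General domain;
- judged unrelated, but leading to treatment or study discontinuation: counted in the General domain;
- judged unrelated, with no discontinuation: not on the key-event list.

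In all three cases it appears in the registry summary under SAP 6.19, which covers every serious event by treatment group and Preferred Term.

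**The case against.** The strongest reply is that the 6.17 list is a short extract and not the safety analysis. CPMP SAP Version 5 holds the ECG analysis and may already tabulate absolute QTcF by arm; it was not available for this review. Section 6.17 says only that the result may be reported, and no passage ties a decision rule to it. A change criterion also has a purpose: it adjusts for where the participant started, and any such rule will sometimes count a low final value and pass over a higher one. If the trial's QTc entry limit, which these documents do not show, is low, few participants can have a baseline in the affected range.

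Most of this stands, and it limits the point to the key-event list. It does not explain why that list should judge QTc by change alone when its other measured items use levels or categories.

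A reader might also infer that serious strokes and vascular events go uncounted in this trial. The documents do not support that. The General domain counts such events when they are judged related or lead to discontinuation, and the serious adverse event summaries show the rest by arm. Widening the cardiovascular entry would also add background events in both arms, and reasonable statisticians could differ on whether that helps.

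**Conclusion.** The point holds for the SAP 6.17 key-event list. That list has no absolute QTc criterion and names no correction. A post-baseline value above a limit L is therefore not a key safety event when baseline is above L − 60 and the rise is 60 msec or less. For an assumed L of 500 msec that means baselines above 440; for 480, baselines above 420.

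The result rests on an assumed limit. The number of participants affected cannot be estimated, because neither the entry limit nor the baseline QTc distribution is given.

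Two stronger conclusions should not be drawn. The documents do not show that the trial will fail to report high QTc values, because CPMP SAP Version 5 may cover them. Nor do they show that this list decides the proof-of-concept question: Protocol 2.1 refers to the totality of the data.

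The serious-event entry needs only a minor clarification. On the MedDRA-class reading, the list leaves out serious vascular or cerebrovascular events that are judged unrelated and do not lead to discontinuation. Those events are still reported by arm elsewhere.

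**What to change.** In SAP 6.17, define the QTc analysis event as QTcF above a stated absolute limit (for example, more than 500 msec) at any post-baseline ECG, or an increase of more than 60 msec. Report it by arm, with each component shown separately so that the change criterion stays visible on its own. Say how participants already above the limit at baseline, or with no baseline ECG, are classified. If CPMP SAP Version 5 already defines an absolute QTcF category, use that same category and cite it. This is a definition for analysis only and sets no rule for managing participants.

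Separately, state whether the serious cardiac entry means the MedDRA Cardiac disorders class, and whether leaving out unrelated, non-discontinuing vascular and cerebrovascular events is intended.

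The cost is a few lines of SAP text. Protocol 8.2.2 already has QTcF recorded, so no new data are needed. The downside is that slightly more events will be counted in both arms.
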